**Table 9 - Analyses of laboratory variables, vital signs and electrocardiograms**

		DB 24W		OL a	LTE b	DB+OL+LTE c
		Adults	Pediatrics	Adults and Peds Separately		
Laboratory, vital signs, ECG	Descriptive summary d	✓	✓	✓	✓	
	Overtime (by-visit) plot d	✓	✓	✓	✓	
	PCSA (or PCSA-like) shift summary	✓	✓	✓	✓ d	✓ d
DILI	Time to first onset	✓	✓	✓		
	Plot of peak values of ALT versus peak values of total bilirubin	✓	✓	✓		✓
	Return to baseline PCSA status summary	✓	✓	✓		✓

a Cumulative data from 1st dose of rilzabrutinib during OL period. Adult and pediatric populations separately.

b Cumulative data from 1st dose of rilzabrutinib during LTE period. Adult and pediatric populations separately.

c Cumulative data from 1st dose of rilzabrutinib regardless of period. Adult and pediatric populations separately.

d For selected laboratory tests only.

DB = double-blind period; OL = open-label period; LTE = long-term extension; 24W = 24-week double-blind period;

DILI = drug-induced liver injury; ECG = electrocardiograms; PCSA = Potentially Clinically Significant Abnormalities; ALT = alanine aminotransferase.

### 3.6.3.2 SAR-CoV-2 testing

Number (%) of participants who had SARS-CoV-2 testing performed and test result will be summarized during each on-treatment period as well as during last 16 weeks (Week 9 to Week 25) of double-blind on-treatment period.

## 3.7 OTHER ANALYSES

### 3.7.1 PK analyses

Plasma concentrations of rilzabrutinib and its metabolites (eg, PRN834 & PRN4400 if applicable) will be summarized by scheduled visit and nominal sampling time in the PK population (Adult and pediatric population separately) in the rilzabrutinib group, using descriptive statistics such as mean, standard deviation, geometric mean, coefficient of variation, median, minimum and maximum. The mean concentration of rilzabrutinib and its metabolites will be plotted against sampling times. The same analyses will be provided which will include the samples collected within the windows specified in the protocol based on the PK sampling time and the dosing time recorded.

Nominal sampling time is as follows

- Pre-dose at Weeks 1, Week 13, and Week 25 visits.
- Post dose at Week 1 and Week 25 visits,
  - For adults: 2-hour post-dose.
  - For pediatric participants: 0.5-hour, 2-hour, 4-hour and 6-hour post-dose.
- Arbitrary timepoint at Week 53 and early termination visits.

Population PK modeling and other analyses might be pursued for exploratory purpose by the PK group in Sanofi which is not in the scope of this SAP and would be reported separately.

For PRN1008 and PRN834, all concentration values below LLOQ will be treated as zero in all summary statistics excepted for the geometric mean and associated coefficient of variation for which they will be considered as missing. For PRN4400, all concentrations below LLOQ will be treated as LLOQ/2, given it is an endogenous compound.

### 3.7.2 Bruton's Tyrosine Kinase (BTK) Occupancy (at selected sites)

BTK occupancy (%) will be summarized by scheduled visit and nominal sampling time (the same time points as specified in [Section 3.7.1](#)) in the safety population at selected sites in the rilzabrutinib group, using descriptive statistics such as mean, standard deviation, geometric mean, coefficient of variation, median, minimum and maximum. Mean BTK occupancy will be plotted against sampling times.

BTK occupancy (%) below LLOQ will be treated as zero in all summary statistics excepted for the geometric mean and associated coefficient of variation for which they will be considered as missing.

### 3.7.3 Clinical Outcome Assessment

The IBLs, ITP-PAQ, ITP-KIT, EQ-5D-5L, PGIS, PGIS-Fatigue and PGIC are utilized in this study. For continuous variables, the domain score (overall score when applicable) and its change from baseline will be analyzed descriptively for each time point.

When applicable, missing items will be handled based on the specific clinical outcome assessment tool instrument. Subjects missing baseline evaluations would not be included in the analyses.

#### 3.7.3.1 ITP Bleeding Scale (IBLS)

The ITP IBLS (5) is a bleeding assessment system comprising 11 (10 for male) site-specific grades from 0 (none) to 2 (marked bleeding) assessed at nine anatomical sites by history over the previous period (Hx). In addition, two of these sites, skin and oral, were also assessed by physical examination (PE). The ‘worst ever’ bleeding experienced at each site was graded using the same system. Refer to [Section 5.5](#) for an example of the copyrighted scale.

The IBLS were assessed at each visit with a 1-week recall period for Hx. For each participant, an IBLS score at each visit will be calculated by taking the average across 11 items (10 for male and postmenopausal female) at 9 sites (8 for male and postmenopausal female). Specifically,

- IBLS score will be calculated only if it is assessed for  $\geq 1$  anatomic sites at a visit. “Not done” is handled the same as “None” with grade 0 ([Section 5.5.1](#)).
- IBLS score will not be calculated if it is not assessed at any anatomic sites at a visit.

For each patient, a mean IBLS score will also be calculated by taking the average across post-baseline visits during the double-blind on-treatment period.

Frequency and severity of bleeding according to IBLS will be summarized at each visit including IBLS score defined above. Mean IBLS score will also be descriptively summarized. In addition, change from baseline in IBLS score will be compared between rilzabrutinib and placebo in the adult participants at Week 25 ([Section 3.3.1.2.5](#)) and Week 13 ([Section 3.3.1.4.1](#)).

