Appendix 9 Remote Study Visits for Active Participants

1. Remote visit procedures to be performed:

- a. Inform the participant that the study clinic visit will be changed to a remote visit.
- b. Remind the participants of their online options to complete the QOL questionnaires.
 - i. In the event the participant is unable to complete them online, email or mail the QOL Questionnaires to the participant. The participant should keep them and provide the completed questionnaires when they return to the clinic, or the site can send a pre-printed and labeled Airway Bill to return via courier.
- c. Schedule a home-health care nurse to visit the participant and collect the required lab samples.
 - i. Schedule a local lab visit to collect at a minimum the platelet count. Obtain the lab name and information when scheduling the test. If the platelet count cannot be obtained because a lab is not available, please notify your local contract research associate as this is both an efficacy and safety assessment.
- d. Collect the following critical study data via the phone call or video call. Document the conversation of the 5 items below.
 - i. New or changes in AEs/SAEs
 - ii. New or changes in concomitant medications
 - iii. New or changes in immune thrombocytopenia concomitant medications
 - iv. Confirm IMP compliance
 - v. Platelet count (done, yes/no, result and units)

2. Documentation:

- a. Source documents: Continue to observe good documentation practice and record all details of the remote study visit, including:
 - i. Participant Study Identification
 - ii. Date and method of remote visit
 - iii. Site staff who performed remote visit
 - iv. All remote data collected
- b. Electronic Case Report Forms: Enter all data collected within 5 days of the remote visit. Any data not collected should be entered as 'Not done' in the applicable eCRF.
- c. If the participant is not able to complete the QOL electronically, after the participant completes the paper questionnaire, the participant can read their answers to the coordinator over the phone with the coordinator recording the verbal conversation in a telephone report noting the test name, question number and the participant verbal answer. This telephone report will reside with the source data and entered into the electronic data capture system. The data will then later be verified against the original supplied by the participant. This deviation in the process will be noted by the Study Coordinator and documented.

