### 1.2.2.2 Key Secondary Efficacy Endpoints (Blinded Treatment Period)

- Number of weeks with platelet count  $\geq$ 50,000/ $\mu$ L OR between  $\geq$ 30,000/ $\mu$ L and  $<$ 50,000/ $\mu$ L and at least doubled from baseline over the 24-week blinded treatment period in the absence of rescue therapy.
- Number of weeks with platelet counts  $\geq$ 30,000/ $\mu$ L and at least doubled from baseline over the 24-week blinded treatment period in the absence of rescue therapy.
- Time to first platelet count of  $\geq$ 50,000/ $\mu$ L OR between  $\geq$ 30,000/ $\mu$ L and  $<$ 50,000/ $\mu$ L and doubled from baseline.
- Proportion of participants requiring rescue therapy during the 24-week blinded treatment period.
- Change from baseline on Item 10 of the ITP-PAQ (ie, physical fatigue) in adult participants ( $\geq$ 18 years) at Week 13.
- Change from baseline in IBLS assessment at Week 25 (applicable to countries within the EU (EEA countries) and UK only).

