### 3.3.1.2.5 *Change from baseline in Idiopathic Thrombocytopenic Purpura Bleeding Scale (IBLS) assessment at Week 25 (applicable to countries within the EU (EEA countries) and UK only)*

The analysis of this key secondary endpoint is to compare the change from baseline at Week 25 on IBLS score ([Section 3.7.3.1](#)) between the rilzabrutinib treatment group and the placebo treatment group via the primary estimand as defined in [Table 2](#).

Change from baseline in IBLS score at Week 25 will be analyzed in the adult ITT population using the same analysis method as specified in [Section 3.3.1.2.4](#) for change from baseline in ITP-PAQ Item 10 except that Week 25 will replace Week 13.

For pediatric population, descriptive summary will be provided based on observed data.

**Intercurrent events and missing data** will be handled similarly as defined in [Section 3.3.1.2.4](#), except that Week 25 will replace Week 13.

Graphical presentations of the results will be provided as needed for the above secondary endpoints. Sample SAS® code could be found in [Section 5.7](#).

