#### 3.7.3.2 ITP Patient Assessment Questionnaire™ (ITP-PAQ™)

The ITP-PAQ (6, 7) is a disease-specific instrument designed to measure the QoL of adult participants with ITP. The instrument comprises 38 items completed by male respondents and 44 items completed by female respondents. Refer to [Section 5.5](#) for an example of the copyrighted scale.

The ITP-PAQ includes 10 scales,

- Symptoms (6 items, Items 1 to 6),
- Fatigue/Sleep (4 items, Items 7 to 10),
- Bother- Physical Health (3 items, Items 11 to 13),
- Activity (2 items, Items 14 to 15),

- Psychological Health (5 items, Items 16 to 20),
- Fear (5 items, Items 21 to 25),
- Overall QoL (5 items, Items 26 to 30),
- Social Activity (4 items, Items 31 to 34),
- Women's Reproductive Health (6 items, Items 35 to 40), and
- Work (4 items, Items 41 to 44)

The items employ a 4-week recall with responses recorded on 4- to 7-point Likert scales containing 4-7 responses. For example, five response options in a 5-point scale: 1 (never), 2 (rarely), 3 (some of the time), 4 (most of the time), 5 (all the time). The full list of 4- to 7-point scale scores could be found in [Section 5.5.3](#). All item scores are transformed to a 0 to 100 continuum where higher scores represent better QoL and are weighted equally to derive the scale scores.

- Each item score is transformed using the formula, transformed item score =  $100 * [(possible\ maximal\ item\ score - item\ score) / range]$ .
- The Women's Reproductive Health Scale will not be calculated for postmenopausal women.
- “Not applicable” will be treated as missing in Items 41 to 44.
- A scale score will be calculated by taking the average of transformed item scores within that scale if at least 50% of items for that scale are answered.

Each individual scale score and its change from baseline will be descriptively summarized at each visit. In addition, the change from baseline in the transformed score of Item 10 of the ITP-PAQ (i.e. physical fatigue) at Week 13 will be compared between the rilzabrutinib group and the placebo group ([Section 3.3.1.2.4](#)).

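### On a partly completed IBLS form, items marked 'Not done' are scored as no bleeding, so they enter the EU/UK Week 25 key secondary endpoint as observed values and bypass the planned imputation

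*SAP*

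**What the plan says.** SAP 3.7.3.1 sets the scoring. At each visit the IBLS score is "calculated by taking the average across 11 items (10 for male and postmenopausal female) at 9 sites" (eight sites for the reduced form). Three further rules deal with incomplete forms:

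- Minimum data: "IBLS score will be calculated only if it is assessed for" one or more anatomic sites at the visit.
- Unassessed items: "Not done” is handled the same as “None” with grade 0".
- No data at all: "IBLS score will not be calculated if it is not assessed at any anatomic sites at a visit".

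The score feeds a confirmatory test. SAP 1.2.2.2 lists "Change from baseline in IBLS assessment at Week 25 (applicable to countries within the EU (EEA countries) and UK only") among the key secondary endpoints. SAP 3.3.1.2.5 analyses it by ANCOVA in the adult ITT population. Protocol Appendix 10.7 places it last in the testing sequence, and SAP 3.5 tests that sequence at a two-sided 5% level.

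Missing IBLS scores follow SAP 3.3.1.2.4 with Week 25 in place of Week 13. That means worst observation carried forward after late rescue or after discontinuation for lack of response or a related adverse event, and multiple imputation otherwise.

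The other scored questionnaires have higher minimum-data rules. An ITP-PAQ scale is scored only "if at least 50% of items for that scale are answered" (SAP 3.7.3.2), and ITP-KIT requires 75% of items (SAP 3.7.3.3).

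**The concern.** The form in SAP 5.5.1 and Protocol Appendix 1 has separate boxes for 'None' and 'Not Done'. The first is a finding and the second is the absence of one. The scoring rule merges them at the most favourable grade. Because one assessed site is enough for a score, a form that is mostly blank counts as a complete observation.

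This has three consequences. Unassessed items never reach the missing-data methods of SAP 3.3.1.2.4 and 3.3.1.2.5. An understated partial score can lower the worst value that is carried forward, and it enters the imputation model as if fully measured. No planned analysis varies the rule: the Week 13 supplementary analysis in SAP 3.3.1.4.1 uses the same score.

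At stake is how far an EU/UK bleeding claim based on the Week 25 comparison can be trusted. The IBLS summaries by visit and the exploratory IBLS endpoints rest on the same score.

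**Working it through.** The documents give no effect size, standard deviation or power for IBLS, so there is no planned figure to reproduce. The check applies the scoring rule directly.

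**Inputs from SAP 3.7.3.1.** Item grades run from 0 to 2. The denominator is fixed at 11 (or 10). 'Not done' = 0. At least one site must be assessed.

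**Formula under the plan.** Score = (sum of grades over assessed items) / 11.

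**Example, with assumed grades and bleeding unchanged between visits.** Skin examination 2, oral examination 1, skin history 2, oral history 1, all other items 0.

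- All items assessed: (2 + 1 + 2 + 1)/11 = 6/11 = 0.55.
- Two examination items not done at Week 25: (2 + 1)/11 = 3/11 = 0.27.
- Apparent change: 3/11 − 6/11 = −3/11 = −0.27, when the true change is 0.
- Same gap at baseline instead, with Week 25 complete: +3/11 = +0.27, an apparent worsening.

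**Extreme case.** With one item assessed and ten not done, the score cannot exceed 2/11 = 0.18, however severe the bleeding at the other sites.

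**General case.** Suppose a share q of items is not done at Week 25, independently of grade, and the true mean item grade is μ. The expected score is (1 − q)μ, so the spurious change is −qμ. The documents give neither q nor μ. Over an assumed range:

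| q | μ = 0.2 | μ = 0.4 |
|---|---|---|
| 5% | −0.01 | −0.02 |
| 10% | −0.02 | −0.04 |
| 20% | −0.04 | −0.08 |
| 30% | −0.06 | −0.12 |

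**Effect on the comparison of arms.** If q is the same in both arms at Week 25, a true difference in Week 25 means shrinks by the factor (1 − q). If q differs, a difference appears where none exists. With μ = 0.4 in both arms, and q of 20% in one and 10% in the other, it is −0.08 − (−0.04) = −0.04. Either arm could be the one favoured.

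**Same example under a minimum-data rule.** Nine of 11 items assessed is 82%, above 50%, so the visit keeps a score: 3/9 = 0.33. The apparent change is 0.33 − 0.55 = −0.21 instead of −0.27. Averaging assessed items reduces the artefact but does not remove it.

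**The case against.** Much of the opposing case stands.

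- **Whole visits are not affected.** A reader might infer that any missed bleeding assessment counts as no bleeding. The SAP does not say that: a visit with no site assessed has no score and goes to the planned handling. The problem is confined to partly completed forms.
- **The direction is not known.** A reader might infer that the rule manufactures improvement, or favours rilzabrutinib. The documents do not support this. A 'Not done' site with no bleeding changes nothing, gaps at baseline push toward worsening, and no frequencies are given by arm or visit.
- **Remote visits are not a demonstrated cause.** Protocol Appendix 9 opens with "Inform the participant that the study clinic visit will be changed to a remote visit", and one might conclude that such visits yield forms lacking only the examination items. But IBLS is not among the critical data that the appendix lists for collection by call. If it is not collected at all, there is no score. Appendix 10.7 also allows home nurses in the EU.
- **The rule follows the form.** 'None' and 'Not Done' are both printed in the grade 0 column, and SAP 3.7.3 defers missing items to the instrument. That explains the rule but does not justify it: neither document states an instrument rule that equates an unexamined site with no bleeding.
- **'Not done' may mean not indicated.** Grade 1 gastrointestinal bleeding is occult blood, and Protocol Table 1 schedules no stool test. Dropping such items raises scores: four items at grade 1, two at 0 and five not done give 4/6 = 0.67 instead of 4/11 = 0.36. This is a real cost of the alternative and a reason to report both versions.
- **The reach is limited.** The endpoint is for the EU/UK only and last in the sequence, and SAP 3.9 records that the sponsor regards IBLS as not validated.

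**Conclusion.** The point holds for partly completed forms. Unassessed items enter a multiplicity-controlled endpoint as observed absence of bleeding, at the best possible grade, outside the planned missing-data handling and without a sensitivity analysis. The SAP should be changed.

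In the worked example an unchanged participant loses half of the score (0.55 to 0.27). Over the assumed ranges of q and μ, the average spurious change from gaps at Week 25 is −0.01 to −0.12. These figures rest on assumed grades and on gaps that are independent of grade; they are not estimates for this trial. The net effect on the comparison of arms may be attenuation or bias in either direction, and the documents do not allow its size to be stated.

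The primary endpoint and the earlier key secondary tests cannot be affected. One further comparison should be avoided: a single item at grade 2 scores 0.18, and a reader might say that it should be 2.0. Under a 50% minimum that visit would be missing, not 2.0.

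**What to change.** Amend SAP 3.7.3.1 as follows:

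1. Treat 'Not done' as missing.
2. Score the mean of the assessed items only if at least 50% of the applicable items are assessed (6 of 11, or 5 of 10), in line with the ITP-PAQ rule.
3. Send visits below that minimum to the handling already specified in SAP 3.3.1.2.4 and 3.3.1.2.5.
4. Keep the present rule ('Not done' = 0) as a sensitivity analysis.
5. Tabulate 'Not done' by item, arm and visit.

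Do not base the main analysis on items assessed at both baseline and Week 25. It would remove the remaining artefact in the example, but it would also discard new bleeding at any site not done at baseline. The baseline covariate would become specific to each visit, whereas the planned ANCOVA and imputation model use one baseline value.

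The cost is SAP wording and scoring code, with no new data collection. Some scores become missing and are imputed. Scores may run higher if 'Not done' often means not clinically indicated; the sensitivity analysis and the tabulation would show whether this matters.

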#### 3.7.3.2 ITP Patient Assessment Questionnaire™ (ITP-PAQ™)

The ITP-PAQ (6, 7) is a disease-specific instrument designed to measure the QoL of adult participants with ITP. The instrument comprises 38 items completed by male respondents and 44 items completed by female respondents. Refer to [Section 5.5](#) for an example of the copyrighted scale.

The ITP-PAQ includes 10 scales,

- Symptoms (6 items, Items 1 to 6),
- Fatigue/Sleep (4 items, Items 7 to 10),
- Bother- Physical Health (3 items, Items 11 to 13),
- Activity (2 items, Items 14 to 15),

- Psychological Health (5 items, Items 16 to 20),
- Fear (5 items, Items 21 to 25),
- Overall QoL (5 items, Items 26 to 30),
- Social Activity (4 items, Items 31 to 34),
- Women's Reproductive Health (6 items, Items 35 to 40), and
- Work (4 items, Items 41 to 44)

The items employ a 4-week recall with responses recorded on 4- to 7-point Likert scales containing 4-7 responses. For example, five response options in a 5-point scale: 1 (never), 2 (rarely), 3 (some of the time), 4 (most of the time), 5 (all the time). The full list of 4- to 7-point scale scores could be found in [Section 5.5.3](#). All item scores are transformed to a 0 to 100 continuum where higher scores represent better QoL and are weighted equally to derive the scale scores.

- Each item score is transformed using the formula, transformed item score =  $100 * [(possible\ maximal\ item\ score - item\ score) / range]$ .
- The Women's Reproductive Health Scale will not be calculated for postmenopausal women.
- “Not applicable” will be treated as missing in Items 41 to 44.
- A scale score will be calculated by taking the average of transformed item scores within that scale if at least 50% of items for that scale are answered.

Each individual scale score and its change from baseline will be descriptively summarized at each visit. In addition, the change from baseline in the transformed score of Item 10 of the ITP-PAQ (i.e. physical fatigue) at Week 13 will be compared between the rilzabrutinib group and the placebo group ([Section 3.3.1.2.4](#)).

### 3.7.3.3 KIDS' ITP-KIT

The ITP-KIT (8), a disease-specific instrument, used in this study is a child self-report form designed to be completed by children  $\geq 7$  years. It has a total of 27 items among which 26 items are structured as Likert scales with five response options 1 (never), 2 (rarely), 3 (sometimes), 4 (often), 5 (always). An additional “Not applicable” option is available for Items 18 to 26, which is scored as 1, the same as “never”. Item 27 is a descriptive question answered “yes” or “no” which is not included in the calculation of the summary score. Respondents record their disease experience based on a 1-week recall. Refer to [Section 5.5](#) for an example of the copyrighted scale.

The instrument yields a summary KIT score which is the summation of the items converted to a 0 to 100 score with higher scores indicating better disease-specific QoL as follows,

- Summary KIT score =  $100 * \{1 - [(Sum\ of\ all\ valid\ responses - number\ of\ valid\ responses) / (number\ of\ valid\ responses * 4)]\}$ ;

- A minimum data rule of 75% will be applied, meaning that at least 20 items must be completed, or no more than 6 missing values may be present for a respondent's data to be considered useable.

The KIT score and its change from baseline will be descriptively summarized at each visit.

